15.4 Analysis Plan

15.4.1 Efficacy Assessments

Each of the primary and secondary efficacy outcome measures listed in sections 15.2.1 and 15.2.2 will be analyzed for the ITT population. The primary outcome measure also will be analyzed and for the "evaluable" and "expanded evaluable" populations. Each of these analyses will be conducted in two ways: 1) comparing the bupropion and placebo groups independent of

compliance data and 2) comparing the medication-compliant subjects in the bupropion group with both the placebo group and the subjects who were not medication-compliant in the bupropion group. Medication-compliant subjects are defined as individuals testing positive for bupropion or its major metabolite in at least 50% of urine samples (in aggregate) obtained during weeks 1 through 10 and at least 66% of urine samples (in aggregate) obtained during weeks 11 and 12. Finally, the analyses described in section 15.2.3 will be conducted for the ITT population.

While there is every intent to be complete in describing the analyses to be performed, it is not possible to anticipate every contingency and some adjustments may be required to meet constraints posed by the structure of the data.

Statistical tests will be two-sided at a 5% Type I error rate. Confidence intervals will be two-sided with a 95% confidence coefficient.

Primary Efficacy Outcome Measure

The primary efficacy outcome measure is a binary measurement of treatment success or failure, where a subject who successfully achieves two weeks of abstinence during the last two weeks of the investigational product dosing period (Weeks 11 and 12) is scored as a success. During the trial, each participant is asked to provide three urine samples per week. A successful outcome requires (1) all urine samples in the last two weeks are negative for methamphetamine (< 300 ng/mL quantitative result of negative qualitative result) and (2) a minimum of two urines samples collected and tested per each of the last two weeks during investigational product dosing. A subject who drops out before the last 2 weeks of the treatment period is scored as a failure in the analysis. A subject who stays on study to the beginning of Week 11 but who does not provide at least 2 urine samples per week during Weeks 11 and 12 is scored as a failure. The proportion of subjects achieving a successful outcome will be compared between groups using a Chi-square test or Fisher exact test, as appropriate based on the estimated expectation of the contingency table's cell sizes computed from the table's row and column totals.

As a secondary analysis, the individual effects, if any, of age, race, methamphetamine use (18 or less *versus* 19-29 days out of 30 days prior to signing consent), clinical site, diagnosis of adult ADHD, severity of depression (HAM-D score ≤ 12 *versus* >12), bupropion blood levels, and usual route of methamphetamine use (oral/nasal inhalation versus intravenous/smoked) on the primary study group effects will be determined where numbers permit.

Secondary Efficacy Outcomes

Unless the primary response analysis implies the need for a more elaborate model, between group comparisons of the secondary outcomes will be performed as follows:

Outcome Measure (from above)									
A, B, C, E, H, I, J, M, N, O, P, Q, R, T, U, V									
D, S, Y, Z									
F, G, J, K									

Statistical Analysis Method GEE Chi-square or Fisher's Exact tests t-test or appropriate nonparametric test

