^a The family history questionnaire will only be done on subjects who consent to the genetics testing even if they are considered a screen failure for the bupropion/methamphetamine study.

^b An alcohol breathalyzer test will be performed in accordance with institutional policy and state law.

^c The pregnancy test on Day 1 must be performed prior to randomization and administration of the first dose of investigational product.

^d These assessments are performed after the first screening visit

^e Eligibility is checked during screening and at baseline visits as data become available such that if a subject does not meet inclusion or exclusion criteria, the subject is no longer screened.

^f The ASI-Lite will be performed during screening; however, if the entire screening/baseline period takes longer than 14 days, the ASI must be repeated such that the it is collected during baseline.

^g Assay for methamphetamine and creatinine as well as the urine toxicology screen will be performed only for urine samples collected from the subjects who are randomized into the study.

^h Blood for RNA analysis should be collected at the same time of day at every collection time point to control for circadian rhythm effects on expression. One RNA tube will be collected during screening/baseline and at all other time points during the intervention phase of the study.

ⁱ During the intervention phase, blood for bupropion levels will be taken before the daily dose.

^j Investigational product compliance is reviewed at every clinic visit with the subject by self report but the pill count is only done weekly.

^k Two 60 minute early recovery skills group sessions given weekly until randomization occurs. Compliance should be checked at each visit and verified with the CBT attendance log.

¹ These assessments are performed at the last visit of Week 12 or at earlier termination.

^mCBT sessions are performed once a week during the follow-up period.

ⁿ Bupropion/hydroxybupropion will be analyzed after study closure only in those assigned to a bupropion treatment group as a surrogate marker for medication compliance.

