15 ANALYTICAL PLAN

15.1 Statistical Hypotheses

Primary Outcome: It is hypothesized that bupropion, as compared to placebo, will increase the proportion of subjects who achieve abstinence (confirmed by at least two methamphetamine-negative urines and no methamphetamine-positive urines) during the last two weeks (Weeks 11 and 12) for non-daily users.

Secondary Outcomes: It is hypothesized that bupropion, compared to placebo, will be associated with an increase in the proportion of subjects who achieve abstinence (confirmed by at least two methamphetamine-negative urines and no methamphetamine-positive urines) each week during the last two weeks (Weeks 11 and 12) for subjects using methamphetamine 18 or less days during the 30 days prior to the start of signing consent. Secondly, it is also hypothesized that bupropion, as compared to placebo, will increase the proportion of subjects with 21 consecutive days of abstinence during which time all urine drug screens must be methamphetamine-negative (both with and without self report), increase the proportion of subjects who reduce their methamphetamine use as compared to baseline use, increase the weekly mean proportion of methamphetamine non-use days according to self-report alone, increase the proportion of methamphetamine negative urine samples, and improve treatment retention. It is hypothesized that bupropion will reduce the severity of methamphetamine dependence, craving, and comorbidity as assessed by the ASI-Lite, the BSCS, the CGI-S, the CGI-O, and the AISRS. It is further hypothesized that in the evaluable population (as defined in section 15.3), bupropion will be significantly more effective than placebo in those subjects who are medication-compliant compared to either the placebo group or subjects who were not medication compliant. This applies to the primary outcome and all secondary outcomes. Medication-compliant subjects are defined as individuals testing positive for bupropion and/or its major metabolite in at least 50% of urine samples (in aggregate) obtained during Weeks 1 through 10 and at least 66% of urine samples (in aggregate) obtained during Weeks 11 and 12.

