15.5 Sample Size calculation

Sample size estimates were performed using the last two week's abstinence rates from a prior Phase 2 trial examining the efficacy of bupropion for the treatment of methamphetamine dependence. The proportion of successful participants was 0.238 and 0.057 for the bupropion and placebo arms, respectively. The proportion of participants achieving a successful outcome was compared between arms using a two-tailed Fisher's exact test (p = 0.01). For a power of 95% and a Type I error rate of 5%, a sample size of 100 per group (total of 200 subjects) is required.

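### Section 15.4.1 extends the compliance comparison to ITT and expanded evaluable subjects, where one-sided selection on retention favours bupropion; in the evaluable set it is still non-randomised

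*Protocol*

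**What the plan says.** Section 15.4.1 assigns all primary and secondary measures to the ITT population and adds the evaluable and expanded evaluable populations for the primary outcome. Each of these analyses is then run in two ways. The first ignores compliance. The second is "comparing the medication-compliant subjects in the bupropion group with both the placebo group and the subjects who were not medication-compliant in the bupropion group". The same section states: "Statistical tests will be two-sided at a 5% Type I error rate".

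A bupropion subject is compliant if drug or metabolite is found in at least 50% of urines from Weeks 1 to 10 and in "at least 66% of urine samples (in aggregate) obtained during weeks 11 and 12". Table 1, footnote n (Section 13.1), restricts the assay: "Bupropion/hydroxybupropion will be analyzed after study closure only in those assigned to a bupropion treatment group as a surrogate marker for medication compliance".

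Section 15.1 states the related hypothesis, expressly within the evaluable population: "bupropion will be significantly more effective than placebo in those subjects who are medication-compliant compared to either the placebo group". It applies this to the primary and all secondary outcomes. The synopsis likewise compares subsets of the evaluable bupropion group with the evaluable placebo group.

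Under Section 15.3, ITT needs only randomisation and one dose. Evaluable subjects need at least two urines per week in Weeks 11 and 12. The expanded evaluable set allows dropouts. Under Sections 15.2.1 and 15.4.1, a subject who drops out before Week 11 is a failure.

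The effect modifiers listed for the primary outcome include "severity of depression (HAM-D score ≤ 12 *versus* >12), bupropion blood levels, and usual route of methamphetamine use".

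**The concern.** In ITT the two sides of the comparison are not selected alike. A bupropion subject can be shown to meet the late-window rule only by giving urines in Weeks 11 or 12, so the compliant subset is in effect a subset of those retained. Placebo urines are not assayed, so placebo cannot be filtered the same way and keeps its dropouts, all scored as failures. The non-compliant bupropion group would also absorb bupropion dropouts if subjects without late samples are classed there. The expanded evaluable set has the same asymmetry.

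The sections also conflict. Section 15.1 applies the hypothesis to every secondary outcome in the evaluable population, but Section 15.4.1 analyses secondary outcomes in ITT only. Followed literally, it tests the hypothesis for those outcomes only in a population where the comparison is biased.

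At stake is a claim that the drug works if taken, reached at the 5% level by a drug with no effect. Blood level as a modifier of the group effect has a related problem: placebo subjects have no level, and on-treatment levels are drawn only at Weeks 6 and 12, so many dropouts will lack them.

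**Working it through.** **The plan's own figure.** Section 15.5 gives: "The proportion of successful participants was 0.238 and 0.057 for the bupropion and placebo arms, respectively", and "For a power of 95% and a Type I error rate of 5%, a sample size of 100 per group". The mean rate is (0.238 + 0.057)/2 = 0.1475. The pooled two-proportion formula is n = [1.96√(2 × 0.1475 × 0.8525) + 1.645√(0.238 × 0.762 + 0.057 × 0.943)]² / 0.181² = (0.983 + 0.798)² / 0.03276 ≈ 97 per group. Exact two-sided Fisher power at 100 per group is 0.951. The figure reproduces. It concerns the randomised comparison only; the protocol gives no figure for the compliance comparison.

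**Set-up for no drug effect.** Both arms have 100 subjects and the same success rate p, either 0.057 (planning placebo rate) or 0.1475 (mean of the planning rates). Retention r is not given for this trial and is assumed to be 42% to 75%. The lower end is the completion figure for methamphetamine users in Section 4.3. Tests use Chi-square or Fisher by expected cell size, as planned.

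**ITT, compliant versus placebo, adherence independent of abstinence.** All successes are retained, so the compliant subset has expected success p/r while placebo has p.

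| p | r = 75% | r = 42% | False positives favouring bupropion (nominal 2.5%) |
|---|---|---|---|
| 0.057 | 0.076 vs 0.057 | 0.136 vs 0.057 | about 6% to 26% |
| 0.1475 | 0.197 vs 0.1475 | 0.351 vs 0.1475 | about 12% to 64% |

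The last column is from simulation. Exact enumeration, letting 50% to 100% of completers be compliant, shows the dependence on dropout:

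| Dropout | p = 0.057 | p = 0.1475 |
|---|---|---|
| 20% | about 5% | 8–10% |
| 30% | about 7% | 15–19% |
| 40% | about 11% | 25–35% |
| 58% | 24–30% | 52–77% |

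**ITT, compliant versus non-compliant bupropion.** Take p = 0.1475, r = 60%, and 70% of those retained compliant, with dropouts counted as non-compliant. Compliant: 42 subjects, 14.75 × 0.7 = 10.3 expected successes, 24.6%. Non-compliant: 58 subjects, 14.75 × 0.3 = 4.4 expected successes, 7.6%. The false-positive rate is about 64%. At p = 0.057 and r = 75% it is about 7%.

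**Evaluable set, adherence independent of abstinence.** Dropouts leave both arms, so both expected rates are p/r. False positives favouring bupropion are about 1% to 3%, close to nominal.

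**Evaluable set, adherence linked to abstinence.** Assume 90% of abstinent and 60% of other completers are compliant. At p = 0.1475 and r = 60%, success among completers is s = 0.246. The compliant rate is 0.9s/(0.9s + 0.6(1 − s)) = 0.328, against 0.246 in evaluable placebo. Over the same retention range, and at both values of p, false positives versus placebo are about 7% to 16%. The non-compliant bupropion rate is 0.1s/(0.1s + 0.4(1 − s)) = 0.075, so that contrast (0.328 versus 0.075) is more distorted still.

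**The case against.** The strongest reply is that the formal hypothesis is limited to the evaluable population, as is the synopsis. A reader who starts from the words quoted from Section 15.1 might infer that the hypothesis itself sets compliant subjects against the whole placebo group. It does not: dropouts before Week 11 are removed from both arms there, and the dropout mechanism disappears. This stands. The dropout bias belongs to the extension in Section 15.4.1.

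Three further inferences are not supported:

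- That every dropout is non-compliant by definition. The rule is a percentage of samples obtained. With none in Weeks 11 and 12 it is 0/0, and no rule is given. A subject who leaves in Week 11 after one drug-positive urine could be compliant and still a failure.
- That Section 15.2.3, items ii and iii, tests whether adherence goes with abstinence. Those items relate drug-positive urines to baseline use days and to screening methamphetamine results, not to on-treatment abstinence.
- That the bias must be very large. The higher figures need heavy dropout, or a null success rate of 14.75%, above the 5.7% planned for placebo. The 42% completion figure describes users in treatment generally. The 90%/60% split has no source in the protocol.

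The comparison is also secondary, and Section 15.4.1 first compares the arms without regard to compliance. That limits the damage but does not justify 5% tests of a comparison that randomisation does not protect.

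**Conclusion.** The point holds for the ITT and expanded evaluable comparisons in Section 15.4.1, which conflict with the evaluable-only limit in Section 15.1 and the synopsis. The ITT comparison favours a drug with no effect. The sizes worked above were computed for the primary binary outcome only and rest on assumed retention and adherence. For the expanded evaluable set and the secondary outcomes the direction is argued, not computed.

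In the evaluable set the error rate is near nominal if adherence is independent of abstinence. The comparison is still non-randomised, and the excess under a link is a matter of assumption.

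The primary ITT test between randomised arms is unaffected. This is a moderate defect in a secondary analysis, not a threat to the main result.

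**What to change.** 1. Reconcile the synopsis, Section 15.1 and Section 15.4.1 on the population, and drop the compliance comparison from the ITT and expanded evaluable populations.
2. In the evaluable set, report compliant bupropion, non-compliant bupropion and placebo results descriptively, labelled exploratory and non-randomised. Give no p-values, and remove the claim of significantly greater effectiveness from Section 15.1.
3. State how subjects with no Week 11–12 samples are classed. This matters for any compliance proportion taken over all randomised subjects.
4. Optionally, for the primary binary outcome, add a randomisation-based complier estimate as a sensitivity analysis: the ITT difference divided by the proportion of the bupropion arm meeting the compliance rule, with a 95% interval. State that it assumes no drug effect below the threshold. That is doubtful for partial takers, who are exposed, and the estimate may then be too large.
5. Remove bupropion blood levels from the modifiers of the group effect and analyse them within the bupropion arm only.

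The cost is wording and a few lines of code; the urine assays are unchanged. The downside is that the compliance result can no longer support a formal efficacy claim.

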2 STUDY SCHEMA

3 PROTOCOL SYNOPSIS

STUDY OBJECTIVES: The primary objective of this study is to assess the efficacy of bupropion in reducing methamphetamine use in subjects with methamphetamine dependence who report using methamphetamine 29 or less days during the 30 days prior to signing consent. It is hypothesized that bupropion, compared to placebo, will be associated with an increase in the proportion of subjects who achieve abstinence (confirmed by at least two methamphetaminenegative urines and no methamphetamine-positive urines) each week during the last two weeks (Weeks 11 and 12) for non-daily users. Secondary objectives include but are not limited to: assessing the success or failure to achieve abstinence (confirmed by at least two methamphetamine-negative urines and no methamphetamine-positive urines) each week during the last two weeks (Weeks 11 and 12) for subjects using methamphetamine 18 or less days during the 30 days prior to signing consent, assessing the safety of bupropion in this study population, assessing other measures of efficacy of bupropion in reducing methamphetamine use or craving, and other psychological assessments of methamphetamine dependence. In addition, if efficacy findings are promising, preliminary evaluations of the genetic markers associated with a positive clinical outcome or predictive of bupropion safety and efficacy including associations with bupropion pharmacokinetics (PK) may be performed.

STUDY DESIGN: This is a double-blind, placebo-controlled, parallel-group design study in which, after an up to 4-week screening period which includes a 2-week baseline assessment period, 200 subjects will be randomly assigned in an approximately 1:1 ratio to either receive placebo or bupropion (100 subjects per group) daily for 12 weeks, with follow-up assessments weekly for 4 weeks after completion of study interventions. Adaptive randomization will be used to balance study intervention groups within each clinical site, based on methamphetamine use (18 or less days *versus* 19-29 days out of 30 days prior to signing consent), severity of depression symptoms [Hamilton Depression Rating Scale (HAM-D) score ≤ 12 *versus* >12], and presence of adult Attention Deficit/Hyperactivity Disorder (Adult ADHD Clinical Diagnostic Scale - ACDS).

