ANALYSIS: Each of the primary and secondary outcome variables will be analyzed using appropriate statistical methods for the intention-to-treat (ITT) population and for the evaluable population. The ITT population includes subjects who are randomized and receive at least 1 dose of investigational product. The evaluable population is those subjects who meet the eligibility criteria, receive at least 4 weeks of investigational product, and provide at least 2 urine samples per week that were analyzed for methamphetamine during the last two weeks of investigational product dosing period (Weeks 11 and 12). The proportions of subjects who achieve abstinence during Weeks 11 and 12 will be compared between groups using either the Chi-square test or Fisher exact test, as appropriate based on the estimated expectation of the contingency table's cell sizes computed from the table's row and column totals. The effect, if any, of age, race, usual route of methamphetamine use (oral/nasal inhalation versus intravenous/smoked), or clinical site on the primary intervention effect will be determined. Interactions of intervention group with methamphetamine use (18 or less days versus 19-29 days out of 30 days prior to signing consent), severity of depression (HAM-D score ≤ 12 versus >12), and presence of adult ADHD will also be assessed. Statistical tests will be two-sided at a 5% Type I error rate. Ninety-five percent confidence intervals will be two-sided. In addition, all of the above-mentioned endpoints will be compared in a medication-compliant subset of the evaluable bupropion group, a medication non-compliant subset of the evaluable bupropion group, and the evaluable placebo group. Medication-compliant subjects are defined as individuals testing positive for bupropion and/or its major metabolite in at least 50% of urine samples (in the aggregate) collected during

study weeks 1-10 and in at least 66% of urine samples (in the aggregate) collected during weeks 11 and 12.

Summaries of the baseline characteristics of the subject population in both intervention groups will be prepared, for both the ITT and evaluable subject populations. A summary will be prepared to show dropouts/retention over time in each intervention group and for major subgroups. Investigational product compliance of each group will be summarized.

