- Y. Proportion of subjects who met the criteria for being abstinent according to the primary outcome measure during Weeks 11 and 12 who continue to be abstinent Weeks 13 through 16 as determined by self-report and confirmation by methamphetamine negative urine sample.
- **Z.** Proportion of subjects who met the criteria for being abstinent according to the primary outcome measure who continue to be abstinent Weeks 13 through 16 as determined by self-report alone.

The proportions will be calculated using the number of subjects who meet the criteria for continued abstinence as described above by the number who were abstinent during weeks 11 and 12 as defined by the primary outcome measure.

Plasma Levels of Bupropion and BDNF

Bupropion is primarily metabolized in human liver by CYP 2B6, an isoform that shows high interindividual variability in expression and catalysis which has been hypothesized to account for the variability in treatment response and toxicity associated with bupropion. Rapid clearance of bupropion via hydroxylation could account for treatment failure, likewise, slow clearance could account for toxicity. Recently, the 6B haplotype of CYP 2B6 has been shown to be a significant predictor of bupropion hydroxylation in human liver microsomal preparations, thus suggesting that individuals with this haplotype may be poorer responders to treatment. At steady state, the mean C_{max} following a 150-mg dose of bupropion every 12 hours is 136 ng/mL. Bupropion plasma levels will be examined for correlation to CYP 2B6 haplotypes and to treatment success.

Elevated plasma BDNF levels are associated with methamphetamine neurotoxicity, and are known to decline during abstinence from methamphetamine. Since bupropion also has an independent effect on BDNF, plasma samples will be tested for bupropion level at the same timepoints as plasma for BDNF is obtained. This will allow the evaluation of whether BDNF is affected differently in subjects receiving bupropion compared to those receiving placebo, and whether this effect influences methamphetamine use or abstinence. In addition, it is also hypothesized that methamphetamine users who have the BDNF 66Val homozygote will be more likely to benefit from bupropion than those who do not.

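### Section 15.4.1 lists bupropion blood level as a modifier of the group effect, but it is a post-randomisation variable that is effectively zero in placebo, so that modification cannot be estimated

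*Protocol*

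**What the plan says.** The primary analysis is an unadjusted between-group comparison: "The proportion of subjects achieving a successful outcome will be compared between groups using a Chi-square test or Fisher exact test". The next paragraph of 15.4.1 adds a secondary analysis, to be done as far as the counts allow. It covers age, race, baseline methamphetamine use, site, adult ADHD and HAM-D severity, and then "bupropion blood levels, and usual route of methamphetamine use (oral/nasal inhalation versus intravenous/smoked) on the primary study group effects will be determined". No model is named, and blood level is not restricted to the bupropion arm.

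The synopsis describes the same analysis with a shorter list: age, race, route, "or clinical site on the primary intervention effect will be determined". It then lists interactions of group with baseline use, depression severity and ADHD. Blood level is in neither synopsis list.

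A separate use of the levels is planned in 15.2.2, under the paragraph on plasma bupropion and BDNF: "Bupropion plasma levels will be examined for correlation to CYP 2B6 haplotypes and to treatment success". That sentence does not say which arm or arms it covers.

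**The concern.** Every other factor in the 15.4.1 list is fixed at or before randomisation and varies in both arms, so asking whether it alters the bupropion-placebo difference makes sense. Blood level meets neither condition.

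- **Timing.** Samples are taken before dosing and at Weeks 6 and 12 (synopsis, Genetics Evaluation; sections 13.3 and 13.6.9). The pre-dose sample should carry no drug, because bupropion use in the previous 30 days is an exclusion (section 9.2, criterion 14). The informative values come after randomisation. The Week 12 sample falls inside or at the end of the Weeks 11-12 outcome window: section 13.3 prefers the first visit of that week, while the Table 1 footnote says the last visit or earlier termination.
- **Placebo.** Placebo subjects receive no bupropion, and bupropion-containing products are prohibited on study (section 12.13). A level of zero in placebo is an inference from this design, but a firm one.

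At stake is a secondary table that appears to test whether the treatment effect depends on exposure, when it either cannot be fitted or answers another question. A group term that vanishes, or turns significant, after adjustment for level could be misread as evidence about the primary result.

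**Working it through.** **1. The plan's own figure.** Inputs from section 15.5: "The proportion of successful participants was 0.238 and 0.057 for the bupropion and placebo arms, respectively", and "For a power of 95% and a Type I error rate of 5%, a sample size of 100 per group". From 15.4.1: "Statistical tests will be two-sided at a 5% Type I error rate". Exact enumeration at 100 per group gives Fisher power of 95.07%, which reproduces the stated 95%. The uncorrected chi-square gives 96.8%, and 94.5% with the Yates correction. The sample size is sound and is not in question.

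**2. Is modification by level estimable?** Let t = 1 for bupropion and 0 for placebo, and let L be the level, with L = 0 whenever t = 0. Then t × L = L for every subject. The columns [1, t, L, t × L] contain a duplicate, so the rank is 3 of 4. No group-by-level effect can be separated from the level slope within the bupropion arm.

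**3. What the group term means if level is a covariate.** In logit P = a + b·t + c·L, placebo gives a, and a bupropion subject with level L gives a + b + c·L. So b contrasts placebo with a bupropion subject extrapolated to L = 0.

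**4. Size of the distortion (simulation; 100 per arm, 1,000 runs per setting).** Assumptions not found in the documents:
- A patient factor u, standard normal, acts on success as logit P = a(arm) + link × u. Each a(arm) is calibrated to the stated success rate.
- In bupropion, L = exp(0.6u) in units of the median level; in placebo, L = 0.
- Every bupropion subject has a level, and the level is fully determined by u. Noise in the level would dilute the effect of a given link.

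Percentage of runs with a significant group term, without level → with level:

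| Scenario | link 0 | 0.5 | 1.0 | 1.5 |
|---|---|---|---|---|
| Planned effect, 0.238 vs 0.057 | 97 → 79 | 97 → 31 | 96 → 5 | 96 → 12 |
| No effect, 5.7% both arms | 3 → 5 | 2 → 6 | 2 → 17 | 2 → 38 |
| No effect, 15% both arms | 5 → 4 | 4 → 18 | 5 → 54 | 4 → 88 |
| No effect, 23.8% both arms | 5 → 5 | 4 → 28 | 4 → 78 | 5 → 96 |

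Under the planned effect, the median group log-odds ratio without level is about 1.65. With level it is 1.71, 0.95, 0.15 and -0.72 across the four links. In the no-effect rows with a link, the spurious group effect is mostly apparent harm, because level was positively linked to success; the opposite link would give apparent benefit.

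**5. Why power falls even with no link.** Extrapolating the bupropion arm to L = 0 multiplies the variance of its fitted log-odds by 1 + mean²/variance of L. For a log-normal with log-SD 0.6 this is 1 + 1/(exp(0.36) - 1) = 1 + 1/0.433 = 3.31.

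**6. Benefit acting wholly through level.** With logit P = logit(0.057) + 1.254·L, calibrated to 0.238 in bupropion, the group term is significant in 95% of runs without level and 4% with it.

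**The case against.** The strongest reply is that 15.4.1 names no model. It speaks only of individual effects as far as the counts allow, it is explicitly secondary, and the same section permits adjustments where the data structure requires them. A rank-deficient term would show itself when fitted, and model choice can be left to an SAP. It stands that the harm is possible rather than certain and that its size depends on assumptions. But the protocol itself names both the factor and the question, and no model choice can estimate modification by a variable that is zero in one arm.

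Several stronger readings are tempting, and the documents do not support them.
- *The primary result could be erased or fabricated.* It could not: the primary test does not include level.
- *Adjusting for level removes the group effect by construction.* That holds only if all benefit acts through the measured level. With no link, the group term is still significant in 79% of runs. Section 4.2.3 also describes active metabolites at plasma concentrations as high as or higher than the parent drug's.
- *Early leavers necessarily have no level.* Table 1 schedules the plasma sample at Week 12 or earlier termination, although the termination list in 13.4 omits it. Some may be missing, but absence is not built in.
- *Missing levels would be counted as zero.* The protocol states no such rule.
- *The synopsis contradicts 15.4.1.* It is a shorter summary, and an omission there is not a contradiction. It shows only that deletion would bring the two lists closer.

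**Conclusion.** The point holds for a named secondary analysis. As listed, modification of the primary group effect by bupropion blood level cannot be estimated, and this follows from the design alone. If level is put into a model with group, detection of the planned effect falls from about 96% to between 79% and 5% over the links examined. With no true effect, false positives stay near 5% at zero link and rise to between 6% and 96% as the link and the success rate increase. These figures rest on an assumed spread of levels (log-SD 0.6), an assumed strength of the level-prognosis link, complete level data and zero levels in placebo. The documents give no value for the first two. The primary chi-square or Fisher test, its 95% power and the 100 per group are untouched, so this is a correction worth making but not a threat to the main conclusion.

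**What to change.** In 15.4.1, delete blood level from the list of factors examined against the group effect, which also agrees with the synopsis lists, and do not adjust the between-arm comparison for it.

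In 15.2.2, state that the correlation of plasma level with treatment success:
- is done within the bupropion arm only;
- is exploratory and non-randomised;
- adjusts for baseline methamphetamine use;
- does not set missing levels to zero.

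The cost is one deleted phrase and one or two added sentences. No new data are needed and the sample size does not change. Nothing estimable is lost, because the exposure-response question stays in 15.2.2. CYP2B6 genotype is not proposed as a substitute modifier: genotyping depends on a separate, optional consent (section 14.3) and on favourable efficacy findings (section 13.6.30).
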